10.2.2. Treatment States for Concomitant Medication Data

This study is a single dose two period crossover study. As such, Concomitant Medications will be attributed to the treatment received within the relevant study period based on the dates and times of the Concomitant Medications in relation to dosing date and time. This is as per IDSL dataset standards. This is detailed in the table below.

10.2.2.1. Treatment States for Concomitant Medication Dates

Treatment State	Definition
Pre-Treatment	CM Start Date / Time < Study Treatment Start Date / Time (Period 1)
On-Treatment (Period 1)	
If CM Start Date / Time is on or after Study Treatment Start Date / Time (Period 1) & before Study Treatment Start Date / Time (Period 2).
 
Study Treatment Start Date / Time (Period 1) \leq CM Start Date / Time < Study Treatment Start Date / Time (Period 2)
 
For randomised subjects, this derivation ensures that CMs starting on or after the Period 1 dose up until the Period 2 dose will be captured and assigned to the Period 1 treatment group.

On-Treatment (Period 2)	
If CM Start Date / Time is on or after Study Treatment Start Date / Time (Period 2) & before Follow-Up.
 
Study Treatment Start Date / Time (Period 2) \leq CM Start Date / Time \leq Follow-Up Date
 
For randomised subjects, this derivation ensures that CMs starting on or after the Period 2 dose up until the Follow-up Visit will be captured and assigned to the Period 2 treatment.

Study Day	Should relate to day since first dose i.e the day of the dose administered during Period 1 should be 'Day 1'.
Period Day	Day within the treatment period, for example, Period 1 Day 1 or Period 2 Day 1

10.3. Appendix 3: Data Display Standards & Handling Conventions

10.3.1. Study Treatment & Sub-group Display Descriptors

Treatment Group Descriptions			
RandAll NG		Data Displays for Reporting	
Code	Description	Description	Order ^[1]
A	Placebo	Placebo	1
B	GSK2586881 0.8 mg/kg	GSK2586881 0.8 mg/kg	2

1. Order represents treatments being presented in TFL, as appropriate.

10.3.2. Baseline Definition & Derivations

10.3.2.1. Baseline Definitions

For all endpoints (expect as noted in baseline definitions) the baseline value will be the latest pre-dose assessment. Baseline definitions are applicable to each period.

Parameter	Study Assessments Considered As Baseline		Baseline Used in Data Display
	Screening	Day 1 (Pre-Dose) Time T0	
Safety			
PASP	X	X	T0
Oxygen Saturation		X	T0
Labs	X		Screening
ECGs	X ¹	X	T0
Vital Signs	X ¹	X	T0
Biomarkers/Pharmacodynamic			
RAS peptides		X	T0
Other biomarkers		X	T0
Ventilatory parameters		X	T0

¹Unless otherwise stated, the mean of replicate assessments at any given time point will be used as the value for that time point.

For statistical analyses (for example, Bayesian mixed model for PASP):

- Baseline is defined as the measurement taken pre-dose during each treatment period (i.e., time T0). This can also be referred to as '**period-specific baseline**'.
- Subject-level baseline** is defined as the mean of the two period-specific baseline readings (the pre-dose T0 reading from each of the two treatment periods) for each subject.

- Period-level baseline (or 'adjusted period-specific baseline') is defined as the difference between the baseline ('period-specific baseline') and 'subject-level baseline' for each period and each subject (i.e., the 'period-specific baseline' minus 'subject-level baseline' in each period).

The statistical modelling will include terms for 'subject-level baseline' and 'adjusted period-specific baseline'.

10.3.2.2. Derivations and Handling of Missing Baseline Data

Definition	Reporting Details
Change from Baseline	= Post-Dose Visit Value – Baseline [Ti – T0]

NOTES :

- Unless otherwise specified, the baseline definitions specified in Section 10.3.2.1 Baseline Definitions will be used for derivations for endpoints / parameters and indicated on summaries and listings.
- Unless otherwise stated, if baseline data is missing no derivation will be performed and will be set to missing.
- The baseline definition will be footnoted on all change from baseline displays.

10.3.3. Reporting Process & Standards

Reporting Process	
Software	

 • The currently supported versions of SAS software will be used to perform all data analyses. Generate tables, figures and listings. • The latest version of R (or alternative supported available packages) will be used in sample size re-estimation for the interim analysis 	
Reporting Area	
HARP Server	: UK1SALX00175.corpnet2.com
HARP Area	: \ARPROD\GSK2586881\204987\Internal_01 : \ARPROD\GSK2586881\204987\Internal_02 : \ARPROD\GSK2586881\204987\Final_01
QC Spreadsheet	: \ARWORK\GSK2586881\204987\Internal_01\documents : \ARWORK\GSK2586881\204987\Internal_02\documents : \ARWORK\GSK2586881\204987\Final_01\documents
Analysis Datasets	

 • Analysis datasets will be created according to Legacy GSK A&R dataset standards (Integrated Data Standards Library) • RAS Peptide data samples for Ang II, Ang(1-5) and Ang(1-7) will be processed by Q2 and data provided to GSK Data Management. • Surfactant Protein D samples and Immunogenicity samples will be processed by GSK and data will be provided to GSK Data Management • Pharmacokinetic samples will be processed by Covance and data will be provided to GSK Data Management 	
Generation of RTF Files	

 • RTF files will be generated for the interim and final reporting efforts 	

Reporting Standards	
General	

 The current GSK Integrated Data Standards Library (IDSL) will be applied for reporting, unless otherwise stated: 
 o 4.03 to 4.23: General Principles o 5.01 to 5.08: Principles Related to Data Listings o 6.01 to 6.11: Principles Related to Summary Tables o 7.01 to 7.13: Principles Related to Graphics 	
Formats	

 All data will be reported according to the actual treatment the subject received unless otherwise stated. GSK IDSL Statistical Principles (5.03 & 6.06.3) for decimal places (DP's) will be adopted for reporting of data based on the raw data collected. Numeric data will be reported at the precision collected on the eCRF. The reported precision from non eCRF sources will follow the IDSL statistical principles but may be adjusted to a clinically interpretable number of DP's. 	
Planned and Actual Time	

 Reporting for tables, figures and formal statistical analyses : 
 Planned time relative to dosing will be used in figures, summaries, statistical analyses and calculation of any derived parameters, unless otherwise stated. The impact of any major deviation from the planned assessment times and/or scheduled visit days on the analyses and interpretation of the results will be assessed as appropriate. Reporting for Data Listings: 
 Planned and actual time relative to study drug dosing will be shown in listings (Refer to IDSL Statistical Principle 5.05.1). Unscheduled or unplanned readings will be presented within the subject's listings. Visits outside the protocol defined time-windows (i.e. recorded as protocol deviations) will be included in listings but omitted from figures, summaries and statistical analyses. 	
Unscheduled Visits	

 Unscheduled visits will not be included in summary tables or figures, unless otherwise stated. All unscheduled visits will be included in listings. 	
Descriptive Summary Statistics	
Continuous Data	Refer to IDSL Statistical Principle 6.06.1
Categorical Data	N, n, frequency, %
Descriptive Summary Statistics (Log Transformed Data)	N, n, geometric mean, 95% CI of geometric mean, standard deviation (SD) of logged data and between geometric coefficient of variation (CV _{b/w} (%)): $CV_b (\%) = \sqrt{(\exp(SD^2) - 1) * 100}$ (NOTE: SD is the SD of log transformed data)
Reporting of Pharmacokinetic Concentration Data	
Descriptive Summary Statistics	Refer to IDSL Statistical Principle 6.06.1 Assign zero to NQ values (Refer to GUI_51487 for further details)
Reporting of Pharmacokinetic Parameters	
Descriptive	N, n, geometric mean, 95% CI of geometric mean, standard deviation (SD)

Reporting Standards	
Summary Statistics (Log Transformed)	of logged data and [between and or within] geometric coefficient of variation (CV _{b/w} (%)) will be reported. [1] $CV_b (\%) = \sqrt{(\exp(SD^2) - 1) * 100}$ (SD = SD of log transformed data) [2] $CV_w (\%) = \sqrt{(\exp(MSE) - 1) * 100}$ (MSE = mean square error from mixed effect model of loge-transformed data).
Parameters Not Being Log Transformed	Tmax, first point, last point and number of points used in the determination of lambda_z for listings
Listings	Include the first point, last point and number of points used in the determination of lambda_z for listings and R squared
Graphical Displays	

Refer to IDSL Statistical Principles 7.01 to 7.13.	

10.4. Appendix 4: Derived and Transformed Data

10.4.1. General

Multiple Measurements at One Time Point

 Mean of the measurements will be calculated and used in any derivation of summary statistics but if listed, all data will be presented. If there are two values within a time window the value closest to the target day for that window will be used. If values are the same distance from the target then the mean will be taken. Subjects having both High and Low values for Normal Ranges at any post-baseline visits for safety parameters will be counted in both the High and Low categories of “Any visit post-baseline” row of related summary tables. This will also be applicable to relevant Potential Clinical Importance summary tables.
Study Day

 Calculated as the number of days from randomisation date : 
 Ref Date = Missing → Study Day = Missing Ref Date < Randomisation Date → Study Day = Ref Date – Randomisation Date Ref Date ≥ Randomisation Date → Study Day = Ref Date – (Randomisation Date) + 1

10.4.2. Study Population

Demographics
Age

 GSK standard IDSL algorithms will be used for calculating age where birth date will be imputed as follows: 
 Any subject with a missing day will have this imputed as day '15'. Any subject with a missing date and month will have this imputed as '30th June'. Birth date will be presented in listings as 'YYYY'.
Body Mass Index (BMI)

 Calculated as $\text{Weight (kg)} / [\text{Height (m)}]^2$

Extent of Exposure

 Number of days of exposure to study drug will be calculated based on the formula: Duration of Exposure in Days = Treatment Stop Date – (Treatment Start Date) + 1 Subjects who were randomized but did not report a treatment start date will be categorised as having zero days of exposure.

10.4.3. Safety

ECG Parameters
RR Interval

 IF RR interval (msec) is not provided directly, then RR can be derived as : 
 [1] If QTcB is machine read & QTcF is not provided, then : $RR = \left[\left(\frac{QT}{QTcB} \right)^2 \right] * 1000$ [2] If QTcF is machine read and QTcB is not provided, then: $RR = \left[\left(\frac{QT}{QTcF} \right)^3 \right] * 1000$
Corrected QT Intervals

 When not entered directly in the eCRF, corrected QT intervals by Bazett's (QTcB) and Fridericia's (QTcF) formulas will be calculated, in msec, depending on the availability of other measurements. IF RR interval (msec) is provided then missing QTcB and/or QTcF will be derived as : $QTcB = \frac{QT}{\sqrt{\frac{RR}{1000}}}$ $QTcF = \frac{QT}{\sqrt[3]{\frac{RR}{1000}}}$

Laboratory Parameters

 If a laboratory value which is expected to have a numeric value for summary purposes, has a non-detectable level reported in the database, where the numeric value is missing, but typically a character value starting with '< x' or '> x' (or indicated as less than x or greater than x in the comment field) is present, the number of significant digits in the observed values will be used to determine how much to add or subtract in order to impute the corresponding numeric value. 
 Example 1: 2 Significant Digits = '< x' becomes x - 0.01 Example 2: 1 Significant Digit = '> x' becomes x + 0.1 Example 3: 0 Significant Digits = '< x' becomes x - 1

10.4.4. Pharmacodynamic and Biomarker

Biomarkers
RAS Peptides

 Ang II, Ang(1-5), Ang(1-7)
Disease Biomarker

 Surfactant Protein D
Variance stabilising transformations (e.g. taking natural logarithms of the observed responses) may be implemented on a per endpoint basis, if deemed necessary by the study statistician. If transformations are used the results will be reported on the back-transformed response scales.

10.5. Appendix 5: Premature Withdrawals & Handling of Missing Data

10.5.1. Premature Withdrawals

Element	Reporting Detail
General	
 Subject study completion (i.e. as specified in the protocol) was defined as any subject who completes all phases in the study including the follow-up visit. Withdrawn subjects will not be replaced in the study. All available data from subjects who were withdrawn from the study will be listed and all available planned data will be included in summary tables and figures, unless otherwise specified.

10.5.2. Handling of Missing Data

Element	Reporting Detail
General	
Missing data occurs when any requested data is not provided, leading to blank fields on the collection instrument :
 
 These data will be indicated by the use of a “blank” in subject listing displays. Unless all data for a specific visit are missing in which case the data is excluded from the table. Answers such as “Not applicable” and “Not evaluable” are not considered to be missing data and should be displayed as such.
Outliers	Any subjects excluded from the summaries and/or statistical analyses will be documented along with the reason for exclusion in the clinical study report.
PK	
If dosing and/or sampling times are missing, the relevant concentrations will be deleted from the population PK and PK/PD analysis dataset and summarized in a deletion record listing. Samples listed as having no sample (NS), no result (NR) or insufficient sample (IS) will be excluded from the PK data set and also included in the deletion record listing. GSK2586881 concentrations below the lower limit of quantification (LLQ) for the assay will be reported as NQ (Below Quantification Limit). All NQ values will be set to “.” (missing) in the population PK and PK/PD dataset. Individuals with all plasma concentrations reported as NQ will be included in the data set.
 
For PK/PD graphics only which are generated by S&P, $\frac{1}{2}$ LLQ can be used for NQ PK data to coincide with methods used for Biomarker data as below. Variables relating to different imputation methods for PK data will be available within the derived A&R PKCNC dataset (e.g. differentiating between setting NQ values to missing or $\frac{1}{2}$ LLQ).

Biomarkers	Any values below the Lower Limit of Quantification (LLQ) will be assigned a value of $\frac{1}{2}$ LLQ for display purposes in Figures and for computation of summary statistics. Any values above the Upper Limit of Quantification (ULQ) will be assigned to the ULQ for display purposes in Figures and for computation of summary statistics. If multiple LLQ and /or ULQ values are available per assay

Element	Reporting Detail
	
(for example if multiple runs with different standard curves are utilised) then the LLQ and/or ULQ value used for the above imputation shall be the minimum of the available LLQs and/or the maximum of the ULQs.
 
If the number of LLQ (and/or ULQ) values is large for an individual biomarker then alternative analysis strategies may be required. "Large" is hard to define prospectively and may depend upon the dataset in question but a general rule of thumb is if >30% of values are LLQ and/or ULQ. If "large" numbers of LLQ and/or ULQ values are observed methodologies to summarise and analyse the responses similar to those detailed in "Standards for the Handling of NQ impacted PK Parameters" (Respiratory DB and CPMS - 14th December 2009) may be employed. Any such methodology will be documented in the statistical contributions to the clinical study report.

10.5.2.1. Handling of Missing Dates

Element	Reporting Detail
General	Partial dates will be displayed as captured in subject listing displays.
Adverse Events	
 The eCRF allows for the possibility of partial dates (i.e., only month and year) to be recorded for AE start and end dates; that is, the day of the month may be missing. In such a case, the following conventions will be applied for calculating the time to onset and the duration of the event: 
 Missing Start Day: First of the month will be used unless this is before the start date of study treatment; in this case the study treatment start date will be used and hence the event is considered On-treatment as per Appendix 4: Treatment States and Phases. Missing Stop Day: Last day of the month will be used, unless this is after the stop date of study treatment; in this case the study treatment stop date will be used. Completely missing start or end dates will remain missing, with no imputation applied. Consequently, time to onset and duration of such events will be missing. Start or end dates which are completely missing (i.e. no year specified) will remain missing, with no imputation applied.

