2.3. Study Design

Overview of Study Design and Key Features	
	
The diagram illustrates the study design. It shows a vertical axis for 'Simulated Altitude [m]' with 0m at the bottom and 4000m at the top. A horizontal axis represents 'Time course of events'. The study begins at 0m, indicated by a vertical arrow pointing down. A dashed vertical line at approximately 1500m altitude represents the transition to 'Hypoxia'. The study then proceeds through several time points: T0 (dose at 0m), T1 (start hypoxia at 4000m), T2 (60 mins Echo at 4000m), T3 (10 mins exercise at 4000m, followed by Echo at 4000m), and T4 (return to 0m). The time axis is marked with 15 mins, 30 mins, 60 mins, T2 Echo, 10 mins exercise, T3 Echo, and 30 mins.

	
The above schematic represents Part 1 of the study. It is applicable also to Part 2 of the study, with the following modifications: simulated altitude will be 5000 m, and the T3 echo will be taken 2 minutes into the exercise challenge (rather than at the end of a 10-minute exercise challenge).

Design Features	
 Single centre Randomised Double-blind (sponsor open) Placebo-controlled Two-period crossover Study duration maximum 56 days
Dosing	
 Single IV dose in each study period

Overview of Study Design and Key Features	
Treatment Assignment	
 • Treatment A: Placebo • Treatment B: GSK2586881 0.8 mg/kg • Subjects will be randomised to one of two treatment sequences AB or BA
Interim Analysis	
 • Planned after approximately 10 subjects had completed treatment periods 1 and 2 (Part 1). The study may have been stopped if a reasonable change in PASP was not observed or if a review of safety data suggested a change in the benefit-risk profile. Following the interim, the decision was taken to continue the study with modifications to the protocol (Part 2). • In Part 2 an interim review is planned when approximately 3 subjects have completed treatment periods 1 and 2. A further review may take place when approximately 6 subjects have completed treatment periods 1 and 2, dependent on data observed in the earlier review. Subsequent interim reviews may take place, if deemed appropriate.

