10.1. Appendix 1: Time & Events

10.1.1. Protocol Defined Time & Events

10.1.1.1. Screening and Follow up

Procedure	Screening ¹ (up to 28 days prior to Treatment Period 1, Day 1)	Follow up (7-10 days post last dose)	Notes
Informed consent	X		
Inclusion and exclusion criteria	X		
Demography	X		
Full physical exam, including height and weight	X	X	Height and weight to be measured at screening only. Weight at screening will be used for dosing calculation.
Alcohol, Drugs of Abuse, Smoking test	X		
Medical history (includes substance usage [and family history of premature CV disease])	X		Substances: Drugs, Alcohol, tobacco
Past and current medical conditions [including cardiovascular medical history]	X		
Serum OR urine pregnancy test (WCBP)	X		
HIV, Hep B and Hep C screen	X		
Laboratory assessments (include liver chemistries)	X	X	Non Fasting
Immunogenicity		X	
12-lead ECG	X	X	Tripplicate ECG required at screening.
Vital signs	X	X	Tripplicate vital signs required at screening.
Spirometry	X		
Echocardiogram	X		
Concomitant Medication review	X	X	
Hypoxia chamber plus exercise	X		Part 1: Tolerance to 4000m for 10 mins followed by incremental exercise testing to determine maximum oxygen uptake (VO2max) and calculate 70% of VO2max (to be used for the exercise challenge during the Treatment Periods). Part 2: Tolerance to 5000m for 10 mins followed by incremental exercise testing to determine maximum oxygen uptake (VO2max) and calculate 50% of

Procedure	Screening ¹ (up to 28 days prior to Treatment Period 1, Day 1)	Follow up (7-10 days post last dose)	Notes
Pharmacogenetic sample (PGx)	X		VO2max (to be used for the exercise challenge during the Treatment Periods) Can be taken any time after consent has been signed. Only required once and is optional.
AE/SAE review	X	X	As per timings detailed in protocol Section 7.2.1.1

1. Screening assessments are allowed to be conducted on more than one day

10.1.1.2. Treatment Period 1 and 2

Procedure	Treatment Period 1 and 2 (Washout 3-14 days)										Notes
	Times relative to start of dosing				Hypoxic Challenge ~80 min (Times relative to entry to Chamber)						
	Pre-dose	0h	15 min	15-45 min	0-60 min	60 min	60-70 min	Immediately after exercise	On exit from chamber	After 30 min rest	
Randomisation	X										Treatment Period 1 only. Randomisation can occur up to the day before the first treatment period
Brief physical exam	X										
Vital signs	X			X				X ⁵			X
Immunogenicity	X										
12-lead ECG	X			X							X

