10.2.1.1. Treatment States for AE Dates

Treatment State	Definition
Pre-Treatment	
AE Start Date / Time < Study Treatment Start Date / Time (Period 1)
 
This will apply to all subjects enrolled into the study, including those not randomised. We may have non-randomised and randomised subjects who have pre-treatment AEs/SAEs. For non-randomised subjects these events will be captured in the 'non-randomised' listing. For randomised subjects these events will be captured in summary listings with treatment group='Pre-Treatment'.

On-Treatment (Period 1)	
If AE Start Date / Time is on or after Study Treatment Start Date / Time (Period 1) & before Study Treatment Start Date / Time (Period 2).
 
Study Treatment Start Date / Time (Period 1) ≤ AE Start Date / Time < Study Treatment Start Date / Time (Period 2)
 
For randomised subjects, this derivation ensures that AEs starting on or after the Period 1 dose up until the Period 2 dose will be captured and assigned to the Period 1 treatment.

On-Treatment (Period 2)	
If AE Start Date / Time is on or after Study Treatment Start Date / Time (Period 2) & before Follow-Up.
 
Study Treatment Start Date / Time (Period 2) ≤ AE Start Date / Time ≤ Follow-Up Date
 
For randomised subjects, this derivation ensures that AEs starting on or after the Period 2 dose up until the Follow-up Visit will be captured and assigned to the Period 2 treatment.

Post-Treatment	
If AE Start Date is on or after Follow-Up.
 
AE Start Date > Follow-Up Date
 
There shouldn't be any instances of this. Subjects will return for a follow-up and visit and any AEs would be documented at that point (and hence included in Period 2 treatment group). No further follow-up of patients is required.

Onset Time Since 1 st Dose (Days/Hours/Mins)	
If Study Treatment Start Date / Time (Period 1) ≤ AE Start Date / Time $= AE Start Date / Time - Study Treatment Start Date / Time (Period 1) + 1 \text{ (min)}$
 
Missing otherwise.
 
A calculation to assess the time since the Period 1 dose up until the start time of

Treatment State	Definition

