10.5.2.2. Handling of Partial Dates

Element	Reporting Detail
Concomitant Medications	
Partial dates for any concomitant medications recorded in the CRF will be imputed using the following convention:
 
 If the partial date is a start date, a '01' will be used for the day and 'Jan' will be used for the month If the partial date is a stop date, a '28/29/30/31' will be used for the day (dependent on the month and year) and 'Dec' will be used for the month. 
The recorded partial date will be displayed in listings.

Element	Reporting Detail
Adverse Events	
Any partial dates for adverse events will be raised to data management. If the full date cannot be ascertained, the following assumptions will be made:
 
• If the partial date is a start date, a '01' will be used for the day and 'Jan' will be used for the month.• However, if these results in a date prior to Week 1 Day 1 and the event could possibly have occurred during treatment from the partial information, then the Week 1 Day 1 date will be assumed to be the start date.• The AE will then be considered to start on-treatment (worst case).• If the partial date is a stop date, a '28/29/30/31' will be used for the day (dependent on the month and year) and 'Dec' will be used for the month. 
The recorded partial date will be displayed in listings.

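### The AE partial-date rules do not fit a single-dose crossover: the stop-day cap can put resolution before onset, a second section gives a different stop date, and the start-day rule ignores period

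*SAP*

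**What the plan says.** Section 2.3 describes the design as "Two-period crossover" and the dosing as "Single IV dose in each study period". The schedule in Appendix 1 gives "Washout 3-14 days" between periods and a follow-up visit 7 to 10 days after the last dose. Under section 10.2.1.1 an AE belongs to a treatment according to its start date and time relative to the two doses: events from the first dose "up until the Period 2 dose will be captured and assigned to the Period 1 treatment", and later ones up to follow-up go to the Period 2 treatment. Duration is resolution minus start plus one minute.

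Two sections then deal with incomplete AE dates.

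- Section 10.5.2.1, start day missing: "First of the month will be used unless this is before the start date of study treatment", in which case the treatment start date is used and the event counts as on-treatment. Stop day missing: "Last day of the month will be used, unless this is after the stop date of study treatment", in which case the treatment stop date is used.
- Section 10.5.2.2: partial AE dates are first queried with data management. If the full date cannot be found, a partial start takes day 01 (and January). If that is too early and the event could have been on treatment, "then the Week 1 Day 1 date will be assumed to be the start date". For stops: "If the partial date is a stop date, a '28/29/30/31' will be used for the day", with December named for the month and no cap at the treatment stop date.

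Neither section mentions period, and the SAP does not say which prevails.

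**The concern.** Both sections assume one treatment start, and 10.5.2.1 also assumes one treatment stop. Here there are two dosing days, each both start and stop of its own treatment, and AEs are collected for days after each. A cap at the treatment stop date therefore acts on the dosing day rather than at the end of an exposure interval.

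The start-day rule decides only whether an event is on treatment. In a crossover that is not enough, because both periods are on treatment and what matters is which one. Section 10.5.2.2 calls its on-treatment assignment a worst case, but that does not follow here. In sequence AB (placebo first), a Period 2 event moved to Period 1 leaves GSK2586881 and is counted under placebo; in BA it moves the other way.

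At stake are AE duration, time to onset and the treatment column in which an event is counted in Tables 3.16 to 3.21.

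**Working it through.** **Inputs.** Dose dates 01OCT2016 and 08OCT2016 from the SAP's own examples in 10.2.1.1; the rules quoted above; washout 3 to 14 days, taken as the interval between doses (an assumption); follow-up 7 to 10 days after the last dose.

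**1. The plan's own examples.** End minus start plus one minute reproduces all four: 08:00 to 08:30 gives 0d 0h 31m; Period 1 onset 08:00 to 09:10 gives 0d 1h 11m; 01OCT 08:00 to 08OCT 10:00 gives 7d 2h 1m; 08OCT 08:30 to 10:00 gives 0d 1h 31m. The formulas are sound; the trouble lies in the imputed dates fed to them.

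**2. Stop day missing, 10.5.2.1.** Imputed stop = the earlier of month end and treatment stop date. If an AE starts at least one day after the last dose, the end of its stop month cannot precede its onset and so falls after that dose. The cap therefore always applies, and the imputed stop is always before onset.

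- Example: onset 10OCT, stop OCT2016. Month end 31OCT is after 08OCT, so the stop becomes 08OCT, and 8 − 10 = −2 days.
- With onset at 08:00, the duration formula gives −2d 7h 59m if the imputed stop is timed 00:00, and −1d 8h 0m if timed 23:59.
- Period 1 AEs starting after the dosing day: none fails if the stop date means the last dose. If it means that period's dose, all of them fail (onset 03OCT, stop OCT2016 gives 01OCT, and 1 − 3 = −2 days).

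**3. Same stop under 10.5.2.2.** Filling only the missing day gives 31OCT, 21 days after onset. The two sections differ for every Period 2 AE that starts after the dosing day and has its stop day missing.

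**4. Start day missing.** Imputed start = the later of the first of the month and the treatment start date (Period 1 dose). As the Period 1 dose precedes the Period 2 dose, the result falls before the Period 2 dose exactly when the first of that month does.

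- AE in the calendar month of the Period 2 dose: goes to Period 1, unless that dose was on the 1st.
- AE in a month beginning on or after the Period 2 dose: correctly assigned to Period 2.
- Example: true onset 10OCT, recorded OCT2016, imputed 01OCT, assigned to the Period 1 treatment.
- If the treatment start date is read as the Period 2 dose, the error reverses: 01OCT is before 08OCT, so a Period 1 AE is moved to 08OCT and counted in Period 2.

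**5. How often the start rule misfires.** Take each Period 1 dose day in a 365-day year, washouts of 3 to 14 days (12 values), follow-up at 7 to 10 days and each possible onset day (8 + 9 + 10 + 11 = 38), all weighted equally: 365 × 12 × 38 = 166,440 Period 2 onsets. Of these, 83% go to Period 1; within the calendar month of the Period 2 dose, 96%. These are rates given that the start day is missing. They do not say how often that will happen.

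**6. Weight of one event.** Section 3.1 gives 11 subjects randomised in Part 1 and up to 14 in Part 2. 1/11 = 9.1% and 1/14 = 7.1%. If the subject has no other event of that term, one column loses this amount and the other gains it.

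**The case against.** The best defence is that the rules will rarely be used. The study is single-centre, dosing is on site, AE derivations use clock times, and partial dates are queried before anything is imputed. Nothing in the SAP shows that an unresolved partial date will occur. The listed AE tables are by system organ class and preferred term and do not summarise duration. Recorded partial dates appear in the listings, so a negative duration would be noticed. All of this stands, and it limits the size of the point. It does not make the rule right for the dates that remain.

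It can also be said that 10.5.2.1 serves only time to onset and duration. However, it goes on to set the on-treatment state, and the SAP offers no way to assign a period other than by start date and time.

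A reader might infer more than the text supports:

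- That every Period 2 AE with a missing start day is misassigned. Events in a month beginning on or after the Period 2 dose are not, nor are those after a dose on the 1st.
- That the share of subjects with both doses in one calendar month measures the failure rate. It does not, because the rule also misfires when the doses fall in different months.
- That 10.5.2.2 sends every partial stop to 31 December. That needs a literal reading. The day is said to depend on month and year, which fits keeping a known month. On that reading the two sections also agree on the start date when only the day is missing, provided Week 1 Day 1 means the Period 1 dose day; the conflict is then in the stop date alone.
- That the rules were written for a continuous-dosing parallel study. The Week 1 Day 1 label, which the schedule does not use, the single treatment start and stop, and the citation of Appendix 4 for treatment states that are in Appendix 2 make this plausible, but it is an inference.

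**Conclusion.** The point holds for AE dates still partial after the query. The capped stop rule gives a stop before onset for every AE that starts a day or more after the last dose and has its stop day imputed; this needs no assumption about the calendar. The conflict with 10.5.2.2 over the stop date holds on either reading of that section. The start rule sends Period 2 AEs in the calendar month of the Period 2 dose to the Period 1 treatment, except after a dose on the 1st. This takes the treatment start date to be the Period 1 dose; the other reading moves Period 1 events to Period 2. The 83% and 96% rest on equal weighting of dates and on washout as the dose-to-dose interval.

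Few events are likely to be affected, and the PASP and oxygen saturation analyses are not. It still deserves correction, because the AE tables compare treatments within parts of 11 and at most 14 subjects, and one reassigned event is visible there.

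**What to change.** Keep one AE partial-date rule and delete the other.

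- **Missing stop day:** last day of the recorded month, or the follow-up or study-end date if that falls earlier in the same month; never before the AE start; no cap at the treatment stop date.
- **Missing start day:** use the Period 1 and Period 2 dose dates, the AE stop date and any other recorded information to exclude impossible periods. Where both remain possible, apply one convention stated in advance and flag the event in the AE listing. The rule should not rely on a recorded period for each AE unless the eCRF is confirmed to hold one; the SAP derives period from dates and times only.
- **References:** replace Week 1 Day 1 with the Period 1 or Period 2 dose date, as the rule requires, and change the treatment-states reference in 10.5.2.1 from Appendix 4 to Appendix 2.

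The cost is a short wording change and a small edit to the AE date derivation, made before database freeze. No new data are needed.
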